11.2 ADVERSE EVENT AND SERIOUS ADVERSE EVENT COLLECTION AND REPORTING

The investigator shall maintain and keep detailed records of all AEs in their patient files.

Collection and Reporting of AEs:

The study design is of non-interventional nature and the study is conducted within the conditions of the approved marketing authorisation. Sufficient data from controlled interventional trials are available to support the evidence on the safety and efficacy of the studied BI drug. For this reason the following AE collection and reporting requirements have been defined.

The following must be collected by the investigator in the (e)CRF via EDC system from first intake of Spiriva Respimat prescribed at baseline visit and within 30 days (inclusive) after the last intake:

- all ADRs (serious and non-serious) as soon as possible,
- all AEs with fatal outcome in patients exposed to Spiriva Respimat as soon as possible,
- all AEs which are relevant for a serious ADR or an AE with fatal outcome in patients exposed to Spiriva Respimat as soon as possible

All ADRs including those persisting after study completion must be followed up until they are resolved, have been sufficiently characterized, or no further information can be obtained.

The investigator carefully assesses whether an AE constitutes an ADR using the information below.

Causal relationship of adverse event:

The definition of an adverse reaction implies at least a reasonable possibility of a causal relationship between a suspected medicinal product and an adverse event. An adverse

reaction, in contrast to an adverse event, is characterised by the fact that a causal relationship between a medicinal product and an occurrence is suspected.

Medical judgment should be used to determine the relationship, considering all relevant factors, including pattern of reaction, temporal relationship, de-challenge or re-challenge, confounding factors such as concomitant medication, concomitant diseases and relevant history.

Arguments that may suggest **a reasonable causal relationship** could be:

- The event is **consistent with the known pharmacology** of the drug
- The event is known to be caused by or **attributed to the drug class**.
- A **plausible time to onset of the event** relative to the time of drug exposure.
- Evidence that the **event is reproducible** when the drug is re-introduced
- **No medically sound alternative etiologies** that could explain the event (e.g. preexisting or concomitant diseases, or co-medications).
- The event is typically **drug-related and infrequent in the general population** not exposed to drugs (e.g. Stevens-Johnson syndrome).

Arguments that may suggest that there is **no reasonable possibility of a causal relationship** could be:

- No plausible time to onset of the event relative to the time of drug exposure is evident (e.g. pre-treatment cases, diagnosis of cancer or chronic disease within days/weeks of drug administration; an allergic reaction weeks after discontinuation of the drug concerned)
- Continuation of the event despite the withdrawal of the medication, taking into account its pharmacological properties of the compound (e.g. after 5 half-lives).
- Of note, this criterion may not be applicable to events whose time course is prolonged despite removing the original trigger.
- Additional arguments amongst those stated before, like alternative explanation (e.g. situations where other drugs or underlying diseases appear to provide a more likely explanation for the observed event than the drug concerned).
- Disappearance of the event even though the study drug treatment continues or remains unchanged.

Intensity of adverse event

The intensity of the AE should be judged based on the following:

Mild: Awareness of sign(s) or symptom(s) which is/are easily tolerated

Moderate Enough discomfort to cause interference with usual activity

Severe: Incapacitating or causing inability to work or to perform usual activities

The intensity of adverse events should be classified and recorded according to the above referenced definition in the (e)CRF.

Pregnancy

In rare cases, pregnancy might occur in a study. Once a subject, has been enrolled into the study after having taken Spiriva Respimat, the investigator must report any drug exposure during pregnancy which occurred in a female subject or in a partner to a male subject to the Sponsor by means of Part A of the Pregnancy Monitoring Form. The outcome of the pregnancy associated with the drug exposure during pregnancy must be followed up and reported by means of Part B of the Pregnancy Monitoring Form.

In the absence of a reportable AE, only the Pregnancy Monitoring Form must be completed.

The investigator will report the Pregnancy Monitoring Forms to sponsor as soon as possible via the unique entry point described in the Site Materials.

Reporting of related Adverse Events associated with any other BI drug

The investigator is encouraged to report all adverse events related to any BI drug other than the Spiriva Respimat according to the local regulatory requirements for spontaneous AE reporting at the investigator's discretion by using the locally established routes and AE report forms. The term AE includes drug exposure during pregnancy, and, regardless of whether an AE occurred or not, any abuse, off-label use, misuse, medication error, occupational exposure, lack of effect, and unexpected benefit.

11.3 TIME WINDOWS

To fulfil the regulatory requirements for expedited safety reporting, the sponsor evaluates whether a particular adverse event is "expected" (i.e., is a known side effect of the drug or not). Therefore a unique reference document for the evaluation of expectedness needs to be provided. For the study product, this is the current version of the Japan PI (package inserts). The current versions of these reference documents are to be provided in the Site material.

11.4 DOCUMENTATION OF ADVERSE EVENTS AND PATIENT NARRATIVES

Expedited reporting of serious adverse events (e.g., suspected unexpected serious adverse reactions (SUSARs) to health authorities) will be done according to local regulatory requirements. Further details regarding this reporting procedure are provided in the Site material.

12. PLANS FOR DISSEMINATING AND COMMUNICATING STUDY RESULTS

The progress reports and final reports will be submitted to PMDA in Japan PSR (Periodic safety report). And also the final report will be submitted in re-examination documents. This study is planned for the publication based on the final report.

ANNEX 1. LIST OF STAND-ALONE DOCUMENTS

Number	Document Reference Number	Date	Title
None			

ANNEX 2. ENCEPP CECKLIST FOR STUDY PROTOCOLS

Doc.Ref. EMEA/540136/2009

European Network of Centres for
Pharmacoepidemiology and
Pharmacovigilance

ENCePP Checklist for Study Protocols (Revision 2, amended)

Adopted by the ENCePP Steering Group on 14/01/2013

The European Network of Centres for Pharmacoepidemiology and Pharmacovigilance (ENCePP) welcomes innovative designs and new methods of research. This Checklist has been developed by ENCePP to stimulate consideration of important principles when designing and writing a pharmacoepidemiological or pharmacovigilance study protocol. The Checklist is intended to promote the quality of such studies, not their uniformity. The user is also referred to the ENCePP Guide on Methodological Standards in Pharmacoepidemiology which reviews and gives direct electronic access to guidance for research in pharmacoepidemiology and pharmacovigilance.

For each question of the Checklist, the investigator should indicate whether or not it has been addressed in the study protocol. If the answer is "Yes", the page number(s) of the protocol where this issue has been discussed should be specified. It is possible that some questions do not apply to a particular study (for example in the case of an innovative study design). In this case, the answer 'N/A' (Not Applicable) can be checked and the "Comments" field included for each section should be used to explain why. The "Comments" field can also be used to elaborate on a "No" answer.

This Checklist should be included as an Annex by marketing authorisation holders when submitting the protocol of a non-interventional post-authorisation safety study (PASS) to a regulatory authority (see the Guidance on the format and content of the protocol of non-interventional post-authorisation safety studies). Note, the Checklist is a supporting document and does not replace the format of the protocol for PASS as recommended in the Guidance and Module VIII of the Good pharmacovigilance practices (GVP).

Study title:

Specific Use-Result Surveillance of Spiriva Respimat in asthmatics (patients with severe persistent asthma)

Study reference number: BI Study Number: 205.525

Section 1: Milestones	Yes	No	N/A	Page Number(s)
------------------------------	------------	-----------	------------	-----------------------

Section 1: Milestones	Yes	No	N/A	Page Number(s)
1.1 Does the protocol specify timelines for				
1.1.1 Start of data collection ¹				10
1.1.2 End of data collection ²				10
1.1.3 Study progress report(s)				10
1.1.4 Interim progress report(s)				10
1.1.5 Registration in the EU PAS register				10
1.1.6 Final report of study results.				10

Comments:

none

1 Date from which information on the first study is first recorded in the study dataset or, in the case of secondary use of data, the date from which data extraction starts.

2 Date from which the analytical dataset is completely available.

Section 2: Research question	Yes	No	N/A	Page Number(s)
2.1 Does the formulation of the research question and objectives clearly explain:				
2.1.1 Why the study is conducted? (e.g. to address an important public health concern, a risk identified in the risk management plan, an emerging safety issue)				11
2.1.2 The objective(s) of the study?				13
2.1.3 The target population? (i.e. population or subgroup to whom the study results are intended to be generalised)				16
2.1.4 Which formal hypothesis(-es) is (are) to be tested?				
2.1.5 If applicable, that there is no a priori hypothesis?				

Comments:

none

Section 3: Study design	Yes	No	N/A	Page Number(s)
3.1 Is the study design described? (e.g. cohort, case-control, randomised controlled trial, new or alternative design)				14
3.2 Does the protocol specify the primary and secondary (if applicable) endpoint(s) to be investigated?				14,15

Section 3: Study design	Yes	No	N/A	Page Number(s)
3.3 Does the protocol describe the measure(s) of effect? (e.g. relative risk, odds ratio, deaths per 1000 person-years, absolute risk, excess risk, incidence rate ratio, hazard ratio, number needed to harm (NNH) per year)				

Comments:

none

Section 4: Source and study populations	Yes	No	N/A	Page Number(s)
4.1 Is the source population described?				
4.2 Is the planned study population defined in terms of:				
4.2.1 Study time period?				16
4.2.2 Age and sex?				17
4.2.3 Country of origin?				
4.2.4 Disease/indication?				17
4.2.5 Co-morbidity?				17
4.2.6 Seasonality?				
4.3 Does the protocol define how the study population will be sampled from the source population? (e.g. event or inclusion/exclusion criteria)				15

Comments:

none

Section 5: Exposure definition and measurement	Yes	No	N/A	Page Number(s)
5.1 Does the protocol describe how exposure is defined and measured? (e.g. operational details for defining and categorising exposure)				
5.2 Does the protocol discuss the validity of exposure measurement? (e.g. precision, accuracy, prospective ascertainment, exposure information recorded before the outcome occurred, use of validation sub-study)				
5.3 Is exposure classified according to time windows? (e.g. current user, former user, non-use)				
5.4 Is exposure classified based on biological mechanism of action and taking into account the pharmacokinetics and pharmacodynamics of the drug?				
5.5 Does the protocol specify whether a dose-dependent or duration-dependent response is measured?				

Comments:

none

Section 6: Endpoint definition and measurement	Yes	No	N/A	Page Number(s)
6.1 Does the protocol describe how the endpoints are defined and measured?				
6.2 Does the protocol discuss the validity of endpoint measurement? (e.g. precision, accuracy, sensitivity, specificity, positive predictive value, prospective or retrospective ascertainment, use of validation sub-study)				

Comments:

none

Section 7: Confounders and effect modifiers	Yes	No	N/A	Page Number(s)
7.1 Does the protocol address known confounders? (e.g. collection of data on known confounders, methods of controlling for known confounders)				17
7.2 Does the protocol address known effect modifiers? (e.g. collection of data on known effect modifiers, anticipated direction of effect)				17

Comments:

none

Section 8: Data sources	Yes	No	N/A	Page Number(s)
8.1 Does the protocol describe the data source(s) used in the study for the ascertainment of:				
8.1.1 Exposure? (e.g. pharmacy dispensing, general practice prescribing, claims data, self-report, face-to-face interview, etc.)				18
8.1.2 Endpoints? (e.g. clinical records, laboratory markers or values, claims data, self-report, patient interview including scales and questionnaires, vital statistics, etc.)				
8.1.3 Covariates?				
8.2 Does the protocol describe the information available from the data source(s) on:				
8.2.1 Exposure? (e.g. date of dispensing, drug quantity, dose, number of days of supply prescription, daily dosage, prescriber)				17
8.2.2 Endpoints? (e.g. date of occurrence, multiple event, severity measures related to event)				14
8.2.3 Covariates? (e.g. age, sex, clinical and drug use history, co-morbidity, co-medications, life style, etc.)				17
8.3 Is a coding system described for:				
8.3.1 Diseases? (e.g. International Classification of Diseases (ICD)-10)				19
8.3.2 Endpoints? (e.g. Medical Dictionary for Regulatory Activities (MedDRA) for adverse events)				19
8.3.3 Exposure? (e.g. WHO Drug Dictionary, Anatomical Therapeutic Chemical (ATC)Classification System)				

Section 8: Data sources	Yes	No	N/A	Page Number(s)
8.4 Is the linkage method between data sources described? (e.g. based on a unique identifier or other)				

Comments:

none

Section 9: Study size and power	Yes	No	N/A	Page Number(s)
9.1 Is sample size and/or statistical power calculated?				18

Comments:

none

Section 10: Analysis plan	Yes	No	N/A	Page Number(s)
10.1 Does the plan include measurement of excess risks?				
10.2 Is the choice of statistical techniques described?				
10.3 Are descriptive analyses included?				19
10.4 Are stratified analyses included?				
10.5 Does the plan describe methods for adjusting for confounding?				
10.6 Does the plan describe methods addressing effect modification?				

Comments:

none

Section 11: Data management and quality control	Yes	No	N/A	Page Number(s)
11.1 Is information provided on the management of missing data?				19
11.2 Does the protocol provide information on data storage? (e.g. software and IT environment, database maintenance and anti-fraud protection, archiving)				18
11.3 Are methods of quality assurance described?				20
11.4 Does the protocol describe possible quality issues related to the data source(s)?				20
11.5 Is there a system in place for independent review of study results?				

Comments:

none

Section 12: Limitations	Yes	No	N/A	Page Number(s)
12.1 Does the protocol discuss: 12.1.1 Selection biases? 12.1.2 Information biases? (e.g. anticipated direction and magnitude of such biases, validation sub-study, use of validation and external data, analytical methods)				20
12.2 Does the protocol discuss study feasibility? (e.g. sample size, anticipated exposure, duration of follow-up in a cohort study, patient recruitment)				
12.3 Does the protocol address other limitations?				

Comments:

none

Section 13: Ethical issues	Yes	No	N/A	Page Number(s)
13.1 Have requirements of Ethics Committee/Institutional Review Board approval been described?				20
13.2 Has any outcome of an ethical review procedure been addressed?				20
13.3 Have data protection requirements been described?				

Comments:

none

Section 14: Amendments and deviations	Yes	No	N/A	Page Number(s)
14.1 Does the protocol include a section to document future amendments and deviations?				

Comments:

none

Section 15: Plans for communication of study results	Yes	No	N/A	Page Number(s)
15.1 Are plans described for communicating study results (e.g. to regulatory authorities)?				27
15.2 Are plans described for disseminating study results externally, including publication?				27

Comments:

none

Name of the main author of the protocol: _____

Date: 15/Apr/2015

Signature: _____

ANNEX 3. FLOW CHART OF VARIABLES

1. Observation period

Item	Time	Observation period ¹			
		Before first administration of Spiriva Respimat	4W	12W (or at discontinuation)	52 W (or at discontinuation)
Patient registration	X ²				
Patient demographics	X				
Administration of Spiriva Respimat	X (to be recorded throughout the observation period)				
Medical history/baseline conditions	X				
Previous/concomitant therapies	X (to be recorded throughout the observation period)				
Pulmonary function test					
FEV ₁	(X)	(X)	(X)	(X)	
FVC	(X)	(X)	(X)	(X)	
PEFR ³	(X)	(X)	(X)	(X)	
Asthma severity	X				
Asthma Control Status	(X)	(X)	(X)	(X)	
QOL (ACQ 6 score)	(X)	(X)	(X)	(X)	
Adverse events	X (to be recorded throughout the observation period)				
Laboratory tests ⁴ associated with AE	(X)				
EDC transmitted time ⁵		X		X	

(X): If applicable

1: Time points during the observation period are approximate. Collected data should be reported as of the closest available visit.

Proprietary confidential information © 2015 Boehringer Ingelheim International GmbH or one or more of its affiliated companies

- 2: Patients administered Spiriva Respimat will be registered within 14 days from whenever the day of first administration is possible.
- 3: PEFR is defined as the mean of the PEFR values of the 7 days before each visit.
- 4: When laboratory related AE is reported, Laboratory tests associated with AE are reported.
- 5: eCRF (electronic case report form): Data are to be transmitted immediately after being entered into the eCRF at 12 weeks and 52 weeks after the start of treatment or at discontinuation. In case of occurrence of any adverse events, the data should be immediately entered into the eCRF and transmitted.

APPROVAL / SIGNATURE PAGE

[figure not shown]
[figure not shown]
[figure not shown]
[figure not shown]
[figure not shown]
[figure not shown]
[figure not shown]
[figure not shown]
Document Number: c02810760

Technical Version Number: 1.0

Document Name: non-interventional-study-protocol

Title: Specific Use-Result Surveillance of Spiriva Respimat in asthmatics(patients with severe persistent asthma)

Signatures (obtained electronically)

Meaning of Signature	Signed by	Date Signed
Author-Trial Clinical Monitor		23 Apr 2015 13:19 CEST
Approval-Pharmacovigilance		23 Apr 2015 13:19 CEST
Approval-Team Member Medical Affairs		23 Apr 2015 13:27 CEST
Approval-Therapeutic Area 		23 Apr 2015 13:30 CEST
Approval-EU Qualified Person Pharmacovigilance		23 Apr 2015 13:31 CEST

## **2. LIST OF ABBREVIATIONS**

Include a list of all abbreviations used in the TSAP

Term	Definition / description
AE	Adverse event
CI	Confidence Interval
CTP	Clinical Trial Protocol
CTR	Clinical Trial Report
DM&SM	Boehringer Ingelheim Data Management and Statistics Manual
EMA	European Medicines Agency
FEV 1	Forced Expiratory Volume in one second
FVC	Forced Vital Capacity
ICS	Inhaled Corticosteroids
LABA	Long Acting β2 Agonist
LTRA	Leukotriene Receptor Antagonist
MedDRA	Medical Dictionary for Regulatory Activities
OCS	Oral Corticosteroid
PEFR	Peak Expiratory Flow Rate
PT	Preferred term
PV	Protocol violation
Q1	Lower quartile
Q3	Upper quartile
SA	Statistical analysis
SABA	Short Acting β2 Agonist
SAMA	Short Acting Muscarinic Antagonist
SD	Standard deviation
SMQ	Standardised MedDRA query
SOC	System organ class
TCM	Trial Clinical Monitor
TOC	Table of contents
TSAP	Trial statistical analysis plan

### **3. INTRODUCTION**

The purpose of this document is to provide a more technical and detailed elaboration of the principal features of the analysis described in the protocol, and to include detailed procedures for executing the statistical analysis of the post-marketing surveillance (PMS) data.

This TSAP assumes familiarity with the Clinical Trial Protocol (CTP), including Protocol Amendments. In particular, the TSAP is based on the planned analysis specification as written in CTP Section 9.7 “DATA ANALYSIS”. Therefore, TSAP readers may consult the CTP for more background information on the study, e.g., on study objectives, study design and population, treatments, definition of measurements and variables, planning of sample size.

SAS® Version 9.4 will be used for all analyses.

#### **4. CHANGES IN THE PLANNED ANALYSIS OF THE STUDY**

No change has been made in the planned analyses from the statistical methods described in the CTP.

## **5. ENDPOINT(S)**

### **5.1 PRIMARY ENDPOINT(S)**

There is no primary endpoint for efficacy, the primary objective of the PMS study is the evaluation of safety (see the CTP Section 9.1.2.1).

### **5.2 SECONDARY ENDPOINTS**

The secondary endpoints will be used as stated in the CTP Section 9.1.1.2.

### **5.3 FURTHER ENDPOINTS**

The other endpoints will be used as stated in the CTP Section 9.1.1.3.

### **5.4 OTHER VARIABLES**

#### **Demographic data and baseline characteristics:**

- Sex: male, female
- Age [years]  
Age [years] = Actual age based on the first administration of Spriva Respimat  
[REDACTED]
- Height [cm]
- Weight [kg]  
[REDACTED]
- Body mass index (BMI) [ $\text{kg}/\text{m}^2$ ]  
BMI [ $\text{kg}/\text{m}^2$ ] = weight [kg] / (height [m])  
[REDACTED]
- [REDACTED]
- Smoking status: Never smoked, Ex-smoker, Current smoker, Unknown
- Pack-Years  
[REDACTED]
- [REDACTED]
- Indication for use: Bronchial asthma, Other
- Asthma Severity: Severe persistent, Moderate persistent, Mild persistent, Intermittent, Unknown

- Duration of asthma [years]  
Duration of asthma = [First administration of Spiriva Respimat – Date of indication of asthma + 1 (if negative value, then 1)] / 365.25: Day of indication is 1.  
[REDACTED]

- Number of hospital admission due to asthma in the past year (Statistics and frequency)
- Number of urgent visit to physician due to asthma in the past year (Statistics and frequency)
- Medical history: Yes, No, Unknown  
[REDACTED]

- Concomitant diagnosis: Yes, No, Unknown  
[REDACTED]

- Previous Medication: Yes, No, Unknown  
Note: Previous medications are existing drugs, drugs which administered before initiation of the new anti-asthmatic drug, drugs of unknown starting date.  
[REDACTED]

- Concomitant Medication during treatment of Spiriva Respimat: Yes, No, Unknown
  - Note: Treated during treatment period of Spiriva Respimat regardless of the start and end date of the medication (except for the case that the end date of the medication and the start date of Spiriva Respimat are the same)SABA: Yes, No, Unknown

- Concomitant therapy: Yes, No, Unknown
- Pulmonary Function Test

- Asthma control status at baseline (see the CTP Section 9.1.1.4): Well-controlled, Insufficiently-controlled, Poorly-controlled, Unknown

- Asthma symptoms (in the daytime or at night): Yes, No, Unknown
- Use of reliever: Yes, No
- Limitation of activities, including exercise: Yes, No, Unknown
- PEFR (mean of the 7 days before each visit) [L/min]
- Pregnancy test: Yes, No, Unknown
- ACQ 6 score at baseline (each score and mean of 6 questions)
- Contraindication to Spiriva Respimat: Yes, No

[REDACTED]

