9.7.2 Safety analyses

The safety analysis will include all patients registered in the study and receiving the Spiriva Respimat treatment. In general, safety analyses will be descriptive in nature, will be based on BI standards, and will focus on ADRs related to the Spiriva Respimat treatment.

AEs will be coded using the current version of the Medical Dictionary for Regulatory Activities (MedDRA) and will be based on the concept of treatment emergent AEs. To this end, all AEs occurring between the first intake of Spiriva Respimat prescribed at baseline visit and within 30 days (inclusive) after the last intake will be considered 'treatment emergent'. An AE is considered to be ADR if either the physician who has reported the AE or the sponsor assesses its causal relationship as 'related'.

The frequency of AEs/ADRs will be tabulated by system organ class and preferred term for overall and for subgroups based on the important baseline characteristics.

No imputation is planned for missing AE data except for missing onset dates which will be handled according to BI standard.

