## **7.5 SECONDARY ENDPOINTS**

Effectiveness at each visit in each patient is determined based on the change of asthma control status from baseline. See the assessment table for effectiveness and the CTP Section 9.1.1.4. And it will be performed as well as [Section 5.4](#). Calculate worse odds ratio in each patient characteristic (demographic and existing treatment factor).

Table 7.5: 1 Assessment table for effectiveness

	Well controlled at baseline	Insufficiently-controlled at baseline	Poorly-controlled at baseline
Well controlled after administration	Improvement	Improvement	Improvement
Insufficiently-controlled after administration	Worse	Worse	Improvement
Poorly-controlled after administration	Worse	Worse	Worse

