### **7.8.1 Adverse events**

Unless otherwise specified, the analyses of adverse events will be descriptive in nature. All analyses of AEs will be based on the number of patients with AEs and NOT on the number of AEs.

Furthermore, for analysis of AE attributes such as duration, severity, etc. multiple AE occurrence data on the CRF, will be collapsed into AE episodes provided that all of the following applies:

- The same MedDRA lowest level term was reported for the occurrences
- The occurrences were time-overlapping or time-adjacent (time-adjacency of 2 occurrences is given if the second occurrence started on the same day or on the day after the end of the first occurrence)
- Treatment did not change between the onset of the occurrences OR treatment changed between the onset of the occurrences, but no deterioration was observed for the later occurrence

For further details on summarization of AE data, please refer ([3](#), [4](#))

AE analyses will be carried out after integrating AE data from CRF and AE data from perceive system.

In addition, AEs coded as “no adverse event” will not be included in the AE analyses.

The analysis of adverse events will be based on the concept of treatment emergent adverse events. That means that all adverse events occurring between first drug intake till 30 days after last drug intake will be analysed. For details on the treatment definition, see [Section 6.1](#).

An overall summary of adverse events will be presented.

The frequency of patients with AEs, ADRs will be summarised by primary system organ class and preferred term. Also, the frequency of patients with ADRs will be summarised by primary system organ class, preferred term and the time to first onset date (1 to 30, 31 to 60, 61 to 90, 91 to 180, 181 to 365, >=366 days). Separate tables will be provided for patients with ADRs stratified by various patient subgroups defined in [Section 6.4](#), for patients with serious AEs. Subgroup analysis will display the frequency of patients, percentage (%) and odds ratio with 95%CI. Logistic regression will be used for odds ratio. The ‘unknown’ and ‘missing’ categories are excluded to calculate odds ratio. Patients with ‘priority survey items’ according to the drug’s Risk Management Plan will be summarised separately.

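### SAP 5.4 lists concomitant medication as a baseline characteristic but defines it by use at any time on treatment, so any odds ratio that uses it is open to reverse causation.

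*SAP*

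**What the plan says.** SAP 5.4, under "Demographic data and baseline characteristics", lists "Concomitant Medication during treatment of Spiriva Respimat: Yes, No, Unknown". Its note counts a patient as "Treated during treatment period of Spiriva Respimat regardless of the start and end date of the medication". The one exception is a drug that ended on the day Spiriva Respimat began. A SABA item follows directly in the extracted text ("are the same)SABA: Yes, No, Unknown"). A separate variable covers earlier drugs: "Previous medications are existing drugs, drugs which administered before initiation of the new anti-asthmatic drug, drugs of unknown starting date".

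Two sections of the SAP compute odds ratios by patient factor:

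- **SAP 7.5 (effectiveness).** After the change in asthma control status is defined, the text says "And it will be performed as well as" Section 5.4. It then asks for an odds ratio for *Worse* by each patient characteristic, and describes these as demographic and existing-treatment factors.
- **SAP 7.8.1 (ADRs).** "Subgroup analysis will display the frequency of patients, percentage (%) and odds ratio with 95%CI". Logistic regression is used, unknown and missing categories are left out, and the subgroups are those of Section 6.4, which is not in the public text.

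Protocol 9.7.2 plans the AE and ADR tables overall and "for subgroups based on the important baseline characteristics". SAP 4 declares no change from the protocol's methods.

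**The concern.** A baseline factor must be fixed before the outcome can influence it, and this one is not. Protocol Annex 3 has concomitant therapies recorded throughout the observation period, which Protocol 9.2.3 sets at 52 weeks, so drugs started after an event will be in the data and will count as *Yes*. The route is concrete here: Protocol 9.5 names asthma itself (1.8%) among the frequent ADRs in the Japanese asthma trials, and a drug started to treat that event would then appear as a factor associated with it.

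For *Worse* there is a second problem. Reliever use is one of the three items that define control status in Protocol 9.1.1.4, so on-treatment reliever use is partly the outcome under another name.

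Subgroup tables are where a surveillance study looks for risk groups and interacting drugs. A treatment given because of the event can show up there as a risk factor that does not exist.

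**Working it through.** **Plan's own figures.** The plan gives no figure on this point. The only planned size is 360 enrolled less 60 without data = 300 in the safety set (Protocol 9.5 and abstract), which is consistent and is used below.

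**Inputs, all assumed because the documents give none.** *u* is the share already on the drug at first intake. *f* is the share of the remaining cases (patients with the ADR) who start it after the event. *g* is the share of the remaining non-cases who start it at any time on treatment. The true odds ratio is 1.

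**Formula.** Exposed share among cases: p1 = u + (1 − u)f. Among non-cases: p0 = u + (1 − u)g. Apparent odds ratio: OR = [p1/(1 − p1)] / [p0/(1 − p0)].

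**u = 0.30.** With g = 0, p0 = 0.30 and its odds are 0.30/0.70 = 0.429. With g = 0.10, p0 = 0.37 and its odds are 0.37/0.63 = 0.587.

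| f | p1 | odds in cases | OR, g = 0 | OR, g = 0.10 |
|---|---|---|---|---|
| 0 | 0.30 | 0.429 | 1.00 | 0.73 |
| 0.20 | 0.44 | 0.786 | 1.83 | 1.34 |
| 0.40 | 0.58 | 1.381 | 3.22 | 2.35 |
| 0.60 | 0.72 | 2.571 | 6.00 | 4.38 |

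**Other values of u (0.2 / 0.4 / 0.6).** With f = 0.25, g = 0 gives 2.67 / 1.83 / 1.56, and g = 0.10 gives 1.71 / 1.43 / 1.31. If cases stop Spiriva Respimat early and so have less time to add a drug (f = 0, g = 0.10), the result is 0.64 / 0.78 / 0.84.

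**Could it look like a signal at the planned size?** Take 300 patients, an assumed 10% ADR rate (30 cases, 270 non-cases), u = 0.4, f = 0.5, g = 0. Cases: 21 exposed, 9 not. Non-cases: 108 exposed, 162 not. OR = (21 × 162)/(9 × 108) = 3.50. SE of the log OR = √(1/21 + 1/9 + 1/108 + 1/162) = 0.417, so the 95% CI is 1.54 to 7.93. With exposure fixed at first intake, the cases split 12 and 18 and the OR is 1.00 (95% CI 0.46 to 2.16).

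**Overlap for *Worse*.** In SAP Table 7.5: 1, a patient who is well or insufficiently controlled at baseline is *Improvement* only if well controlled afterwards. Protocol 9.1.1.4 allows well controlled only with no reliever use. For these patients, reliever use once or more a week at the visit makes *Worse* certain. SABA use at any time on treatment is not the same as weekly use at the visit, so exposure and outcome overlap without being identical.

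**The case against.** The strongest reply is that the visible plan never states that on-treatment medication is a factor in any odds ratio.

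- **ADR odds ratios.** The factors are in Section 6.4, which cannot be seen; that gap is not a fault of the plan. Protocol 9.7.2 and SAP 4 suggest baseline factors only. A reader might infer that the ADR tables will certainly carry this bias, but the documents do not show it.
- ***Worse* odds ratios.** Section 7.5 limits the treatment factors to existing ones, and 5.4 uses the same word for previous medication. On that reading on-treatment drugs are out. The reading is plausible but not secure, because 7.5 also refers to 5.4 as a whole.
- **SABA.** A reader might infer a circular analysis of *Worse* by SABA. That needs both the wider reading of 7.5 and the assumption that SABA follows the concomitant-medication note. The second rests on run-on text in a partly redacted list.
- **The overall Yes/No item.** ICS is an entry requirement, so almost every patient will be *Yes* and there is little contrast. The concern is with drug-class items.
- **Direction and size.** An upward bias cannot be assumed. The largest figures hold starts among non-cases at zero over 52 weeks, and the bias can reverse.
- **Descriptive purpose.** Protocol 9.7 foresees no confirmatory testing.

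These points make the concern conditional. They do not defend the definition: no visible text limits the variable to drugs started before the event, and a descriptive odds ratio with a confidence interval will still be read as evidence about risk groups. Previous medication is a usable pre-treatment variable but not a clean substitute, because it takes in drugs of unknown start date and nothing visible requires the drug to be ongoing at first intake.

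**Conclusion.** The concern holds in conditional form. The definition in SAP 5.4 conflicts with the heading it sits under, and it would also conflict with Protocol 9.7.2 if the variable were used as a subgroup factor. Any odds ratio in 7.5 or 7.8.1 that uses it, or a class item under the same rule, is open to reverse causation. On-treatment reliever use set against *Worse* would also overlap with the outcome.

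Under no true association and 30% baseline use, the apparent odds ratio is 1.8 to 6.0 for 20% to 60% post-event starts among cases with none among non-cases, and 1.3 to 4.4 with 10% starts among non-cases. It falls below 1 if cases start the drug less often than non-cases. These figures illustrate the mechanism and do not predict this study's results. Whether the plan actually uses the variable in this way cannot be settled from the public text.

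**What to change.** In SAP 5.4, derive a variable for medication ongoing at first intake of Spiriva Respimat from the recorded dates, by drug class where needed. State in 7.5 and 7.8.1 that only this variable, or other pre-treatment medication, may serve as a medication factor in an odds ratio. In 7.5, say which 5.4 variables the existing-treatment wording covers. Move on-treatment concomitant medication out of the baseline heading and report it descriptively, without odds ratios; this also removes any comparison of *Worse* by on-treatment reliever use.

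The cost is SAP wording and one derived variable, with no new data collection. The downside is that drugs with unknown start dates need a rule. SAP 5.4 now counts them as previous medication. Either keep that rule, accepting that some may have been started later, or class them as unknown, which drops those patients from the odds ratio under 7.8.1. If Section 6.4 already excludes on-treatment medication, the clarification of 7.5 and the change of heading are enough.
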